We subsequently performed several studies which suggest that spinal release of oxytocin represents the protective factor against chronic pain after childbirth. Intrathecal injection of the specific oxytocin receptor antagonist, atosiban, temporarily reverses the blockade of nerve injury induced hypersensitivity in the postpartum period in rats. Similarly, intracerebroventricular administration of the  $\alpha$ -adrenoceptor antagonist, phentolamine, which is known to block the effects of lactation on activation of oxytocin-containing neurons in the paraventricular nucleus (PVN) of the hypothalamus, also temporarily reverses the blockade of nerve injury induced hypersensitivity in the postpartum period in rats. Finally, protection against hypersensitivity from nerve injury is abruptly reversed when pups are separated from dams for 24 hr, and this is accompanied by a large decrease in oxytocin concentration in cerebrospinal fluid. Although we are currently performing more clinical and laboratory studies to further define this mechanism, these data suggest that spinal oxytocin receptor stimulation in the period immediately following delivery protects against the generation of injury-induced hypersensitivity and subsequent chronic pain.

We recently completed a Phase 1 safety study of intrathecal oxytocin and observed no serious adverse events over the dose range studied (5-150  $\mu$ g). One subject at the 150  $\mu$ g dose had transient subjective numbness in sacral dermatomes, but this was preceded by a vasovagal episode beginning just prior to spinal injection, and this did not occur in other subjects at this dose. There were no objective signs of motor or sensory dysfunction in any volunteer, and blood pressure, heart rate, sensorium, corrected QT interval and serum sodium were unaffected.

We anticipate that oxytocin will be effective after spinal injection in humans to acutely relieve chronic neuropathic pain. For these future studies, we will use a cross over, controlled and blinded study of intrathecal oxytocin in patients with neuropathic pain below the umbilicus, with primary outcome being visual analog score for pain and secondary outcomes being areas of increased pain sensation to a normally painful stimulus (hyperalgesia) and pain sensation to what previously was an innocuous stimulus (allodynia).

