#### Safety and Monitoring:

Assessment of Side Effects: Significant side effects are defined as changes > 30% from baseline in the mean arterial pressure, HR, or oxyhemoglobin pulse oximetry < 90. Any unexpected or serious side effects will be reported to the IRB and the FDA within 24 hrs. Peripheral oxyhemoglobin saturation, BP and HR will be measured non-invasively before and 15, 30, 60, 120, 180, 240, minutes after administering spinal oxytocin and the electrocardiogram will be monitored continuously for the duration of the study.

A monitor tracing from the ECG will be recorded at 15 minute intervals for the first hour then hourly until discharge. If either BP or HR change by > 30%, or oxyhemoglobin saturation decreases to less than 90, and require treatment, these vital signs will be repeated at 5-minute intervals until vital signs are stabilized. A screening neurologic exam along with questioning for qualitative symptoms will be performed at 45, 90, 150, 210, and 240 minutes. The screening neurologic test will consist of examining both an arm and leg for deep tendon reflexes (DTR's), light touch, extension/withdrawal strength. In addition we will ask the volunteer about other symptoms to include sedation, anxiety, nausea, GI, bladder, dizziness, extremity weakness, or any other symptom which was not specifically asked. Any symptom proffered will be categorized on a scale of the volunteer's choosing.

Treatment of Side Effects: Mean blood pressure elevations greater than 30% of baseline will be treated with labetalol 5-15 mg IV incrementally until BP elevation is less than 30% elevated. If BP elevation is judged to be due to pain following spinal oxytocin injection, we will treat pain first (at the volunteer's request) and only treat BP elevations if the volunteer has sufficient analgesia (he does not desire additional analgesia). Reductions in mean BP > 30% of baseline will be treated with incremental ephedrine 5-20 mg, IV. Heart rate (HR) reductions or elevations > 30% of baseline will be treated with incremental glycopyrolate 0.2 mg IV or propranolol 0.2 mg IV, respectively. Peripheral oxyhemoglobin desaturation (< 90) will be treated with supplemental oxygen, nasal cannula, face mask, or non-rebreathing mask depending upon the degree desaturation and the response to therapy.

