#### Completion of Day 2 Assessment

1. Vital signs are within 20% of those on admission to the CRU
2. He or she can ambulate without difficulty (no motor, balance affects).
3. Someone other than the subject will take the subject home (requirement for participation).
4. Subject promises to stay home where he or she can be contacted by telephone (requirement for participation).

We will instruct the subject to call us, providing beeper and telephone numbers of the research nurse and the investigators should he have any questions or problems. The research nurse will call the subject at 6 hours and 12 hours post-spinal study drug injection inquiring about any perceived problems.

Study Visit 3: Approximately 24 hours after the spinal oxytocin injection the subject will report to the CTSI CRU to have a blood sample drawn for a Basic Metabolic Panel to assess serum sodium levels.

Study Visit 4: At least one week after Study Visit 2 the subject will return to the CTSI CRU for intrathecal injection of the cross over study solution. All procedures will be the same as Study Visit 2.

Study Visit 5: Approximately 24 hours after the spinal oxytocin injection the subject will report to the CTSI CRU to have a blood sample drawn for a Basic Metabolic Panel to assess serum sodium levels.

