## **RISKS**

Risks of spinal needle insertion include pain on insertion, local bruising or soreness, post-dural puncture headache, and permanent nerve injury. Participants in this study will be informed regarding these risks. Local anesthesia will be used to prevent pain on needle insertion, and a small (#25 or #27) Whitacre tip needle used to minimize local trauma and risk of headache. We routinely telephone all subjects daily for 5 days. Participants will also be contacted weekly for 1 month, then approximately 6 months after the study to inquire regarding local discomfort or headache. There is a risk (less than 1%) of developing a headache from the spinal needles. If a subject develops a headache that does not go away and is bothersome, offer to perform an epidural blood patch. This procedure is 95% effective in treating the headache. Rarely (5 out of 100 times) is a 2nd blood patch needed. Other risks of the epidural blood patch are the same as the spinal. The risk of paralysis, infection or nerve damage from a spinal procedure is extremely rare, less than one chance in 20,000. The numbing medicine that we put under your skin right before the spinal needle is inserted may cause you to have a brief period (about 5 seconds) of mild discomfort. We have had no local discomfort lasting more than 2 weeks and only 1 headache in 438 subjects that required epidural blood patch treatment.

Risks of intrathecal oxytocin include unforeseen toxicity. This drug will be studied under FDA oversight and approval. The safety of spinal oxytocin has been extensively examined in animals, with no evidence of any nerve damage or other lasting effects, the FDA has approved this investigational study for humans, nearly 1000 humans have received spinal oxytocin in China without reported problems, and we did not observe toxicity in the recently completed Phase 1 study and in a study of over 90 subjects undergoing hip replacement surgery at this institution. Although this all suggests that it is safe to administer oxytocin, the exact risks are unknown. We will monitor subjects for many theoretical problems such as level of sleepiness, changes in blood pressure, heart rate and breathing. We will treat any side effects that the subject may experience if the changes are enough to concern us.

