### **Previous Experience in the CRU**

These investigators have, under NIH grant GM48085, regularly performed intrathecal injection studies with novel drugs for intrathecal delivery in healthy volunteers and in patients since 1990. Drugs studied include clonidine, fentanyl, neostigmine, adenosine, ketorolac and oxytocin. In addition, we have studied drugs approved for intrathecal delivery (morphine and bupivacaine) in the CRU. The most common adverse effect from these studies has been mild, transient backache and headache. Persistent headache requiring blood patch has occurred in <1% of subjects, likely reflecting the use of very small gauge (#27), pencil point spinal needles. Drug related adverse effects have included hypotension and bradycardia (clonidine), nausea (fentanyl, neostigmine), mild respiratory depression (fentanyl), transient back and leg pain (adenosine) and one episode of hypotension and bradycardia consistent with a vaso-vagal response to injection (oxytocin). The IRB and FDA recognizes that there are potential risks to these studies and has supported performance of this research in the CRU with the presence of an anesthesiologist and nurse,

appropriate monitoring, intravenous access, and immediate access to appropriate drugs for treatment.

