### **Data Safety Monitoring Plan**

This Phase II trial will be performed with a data safety monitoring committee ([name] and [name].) who is not involved in the study. Data and adverse events will be reported to these individuals quarterly. Adverse events will also be reported to the IRB and the FDA (since trials are being conducted under an IND). Serious adverse events will be reported to all of these groups and the data safety monitoring individuals within 24 hr and the trials halted until feedback is obtained from each. Data and any adverse events will be monitored and reviewed by the PI after treatment of each subject.

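### No common scale is set for symptom ratings, so they cannot be pooled across volunteers, and use of one scale at both injection visits is not clearly required

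*Combined protocol and SAP*

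**What the plan says.** The Safety and Monitoring section fixes when symptoms are asked about: "A screening neurologic exam along with questioning for qualitative symptoms will be performed at 45, 90, 150, 210, and 240 minutes". It also fixes most of what is asked: "we will ask the volunteer about other symptoms to include sedation, anxiety, nausea, GI, bladder, dizziness, extremity weakness", followed by an open item for anything not named. It then leaves the scale to the volunteer: "Any symptom proffered will be categorized on a scale of the volunteer's choosing".

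The same section gives common criteria for a significant side effect, but only for mean arterial pressure, heart rate (both a change of more than 30% from baseline) and oxygen saturation (below 90). None applies to symptoms.

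For the second injection, the Study Visit 4 entry states: "All procedures will be the same as Study Visit 2".

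Under RISKS the plan undertakes monitoring that includes a graded symptom: "We will monitor subjects for many theoretical problems such as level of sleepiness, changes in blood pressure, heart rate and breathing". Under the Data Safety Monitoring Plan, "Data and adverse events will be reported to these individuals quarterly", and the principal investigator reviews data and adverse events after each subject.

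**The concern.** The trial is a crossover in which each volunteer receives both intrathecal saline and intrathecal oxytocin. That layout suits a side-by-side account of symptoms under the two solutions, and the RISKS section acknowledges that the risks of the drug are not fully known. The questions and times are standardised, but the scale for the answers is not. A rating of 3 from one volunteer and of moderate from another cannot be placed in one table, and neither can two numbers from scales with different ranges or anchors.

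What is at stake is how far the symptom ratings can be used: whether anyone can describe how marked symptoms were under oxytocin and under saline across the group, and whether one volunteer's ratings at the two injection visits can be set against each other.

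**Working it through.** No arithmetic applies. The documents give neither a symptom incidence nor any information on which scales volunteers would pick, so the check is a reading of the text.

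**Step 1: is a common symptom scale set anywhere?**

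| Section | Scale or criterion | Applies to |
|---|---|---|
| Safety and Monitoring | Volunteer's choice | Symptoms |
| Safety and Monitoring | Change above 30%, or saturation below 90 | Blood pressure, heart rate, saturation |
| Statistical Rationale | Visual analog scale | Ongoing pain |
| Long-term Follow-up | Verbal score | Pain |
| Data Safety Monitoring Plan | None named | Adverse events |

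None is set. The two scales named elsewhere are for pain only.

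**Step 2: which symptoms does the volunteer's-choice sentence cover?** The word *proffered* has two readings.

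- *Wide:* every symptom reported, prompted or not. All symptom ratings are then on volunteer-chosen scales.
- *Narrow:* only symptoms the volunteer raises. Those are then on volunteer-chosen scales, and the seven prompted symptoms (sedation, anxiety, nausea, GI, bladder, dizziness, extremity weakness) have no stated scale.

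Neither reading yields a common scale. A symptom off the prompted list falls under the volunteer's-choice sentence either way. Numbness is an example. The Background reports "transient subjective numbness in sacral dermatomes" in one Phase 1 subject at 150 µg, preceded by a vasovagal episode and not seen in others at that dose.

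**Step 3: can ratings be pooled across volunteers?** Pooling needs a shared range and shared anchors. The plan supplies neither, so it cannot be done from data collected as written. Some volunteers may happen to choose the same scale, but nothing in the plan brings that about.

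**Step 4: can one volunteer's two visits be compared?** The Study Visit 4 sentence can mean that the volunteer's assessment, scale included, is repeated unchanged. It can also mean that the procedure is repeated, and that procedure is a free choice of scale. On the first meaning the within-volunteer comparison is sound; on the second it is not assured. The text does not decide between them.

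**Step 5: what is unaffected?** Presence or absence of each prompted symptom rests on fixed questions at 45, 90, 150, 210 and 240 minutes and needs no scale. Vital signs, ECG, the neurologic exam, serum sodium and the visual analog pain score are measured separately.

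**The case against.** The strongest case against is that nothing planned depends on these ratings. The Statistical Rationale covers pain only. Significant side effects are defined by vital signs and saturation, and halting of the trial is tied to serious adverse events. The questioning is described as qualitative, and the text never says that the chosen scale measures severity. On this view the procedure is a symptom screen, and a screen needs no common scale. All of those facts stand, and they are why the point is minor. They do not remove it: the plan says symptoms will be placed on a scale, so graded data will be collected, and on unspecified scales those data cannot be summarised for the group.

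A second objection is that the Study Visit 4 sentence most naturally keeps each volunteer's assessment the same, so the within-volunteer contrast survives. That may be right. It would leave pooling across volunteers unresolved, and the requirement is not explicit.

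Three stronger readings are tempting and should be resisted.

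- A reader might infer that a planned safety analysis is invalid. No analysis of symptom ratings is stated, and the documents do not say whether ratings form part of the quarterly reports.
- A reader might infer that oxytocin and saline cannot be compared on symptoms at all. Incidence can be compared, and ratings within a volunteer can be too if the scale is kept.
- A reader might multiply symptoms, times, visits and volunteers and take the product as the size of the problem. That counts questions asked, not ratings affected. An answer of none means the same on any scale, and on the narrow reading the sentence does not govern the prompted questions at all.

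Nor does the remark that "The most common adverse effect from these studies has been mild, transient backache and headache" bear on the scale. It summarises earlier studies of several drugs.

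**Conclusion.** The point holds in a limited form. The plan sets no common scale for symptoms. As written, symptom ratings cannot be pooled across volunteers, and use of the same scale at Study Visits 2 and 4 is not clearly required. The gap exists on both readings of which symptoms the sentence covers.

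This is a minor improvement to the safety data, not an error in a stated analysis. The number of ratings affected cannot be computed from the documents. The conclusion rests on two assumptions: that the scale is meant to grade how marked a symptom is, since no other such measure is given, and that volunteers left to choose will not all choose alike. If either fails, the practical loss shrinks further.

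**What to change.** Replace the sentence on volunteer-chosen scales with:

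> Every symptom reported, whether prompted or volunteered, will be rated by all volunteers on one fixed scale (0-10 verbal severity, 0 = none, 10 = worst imaginable), the same at Study Visits 2 and 4.

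Add one line stating that symptom incidence and maximum rating will be summarised by treatment, descriptively and without a formal test.

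This settles the scope of the sentence, sets a common scale across volunteers, and makes the same scale explicit at both injection visits. A shared scale does not guarantee that volunteers use it identically, but it supplies the common range and anchors that a group summary needs.

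The cost is a case report form change and slightly more structured questioning at times already scheduled. No visit, procedure or treatment rule changes.

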#### Completion of Day 2 Assessment

1. Vital signs are within 20% of those on admission to the CRU
2. He or she can ambulate without difficulty (no motor, balance affects).
3. Someone other than the subject will take the subject home (requirement for participation).
4. Subject promises to stay home where he or she can be contacted by telephone (requirement for participation).

We will instruct the subject to call us, providing beeper and telephone numbers of the research nurse and the investigators should he have any questions or problems. The research nurse will call the subject at 6 hours and 12 hours post-spinal study drug injection inquiring about any perceived problems.

Study Visit 3: Approximately 24 hours after the spinal oxytocin injection the subject will report to the CTSI CRU to have a blood sample drawn for a Basic Metabolic Panel to assess serum sodium levels.

Study Visit 4: At least one week after Study Visit 2 the subject will return to the CTSI CRU for intrathecal injection of the cross over study solution. All procedures will be the same as Study Visit 2.

Study Visit 5: Approximately 24 hours after the spinal oxytocin injection the subject will report to the CTSI CRU to have a blood sample drawn for a Basic Metabolic Panel to assess serum sodium levels.

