## **STUDY DESIGN**

Inclusion Criteria: We request permission to study up to 44 subjects so that we will have 40 evaluable subjects.

1. Male or female  $\geq 18$  and  $< 70$  years of age, with a BMI  $< 40$ .
2. Presence of neuropathic pain for  $> 6$  months, with primary pain area below the umbilicus.

We will focus recruitment efforts on low back pain with a neuropathic component to the lower extremities, but will accept other causes of neuropathic pain.

3. Female subjects of child-bearing potential and those  $< 1$  year post-menopausal, must be practicing highly effective methods of birth control such as hormonal methods (e.g., combined oral, implantable, injectable, or transdermal contraceptives), double barrier methods (e.g., condoms, sponge, diaphragm, or vaginal ring plus spermicidal jellies or cream), or total abstinence from heterosexual intercourse for a minimum of 1 full cycle before study drug administration.

4. Blood pressure (systolic 90-150 mmHg; diastolic 50-90 mmHg) resting heart rate 45-100 beats per minute.

5. All subjects must be vaccinated against SARS-CoV-2, with proof via vaccination card or the NC HHS form.

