### **RANDOMIZATION GROUPS**

A computer generated randomization will be used to determine the group for each subject. Subjects will be randomized to receive an intrathecal injection of the saline placebo or 100 µg oxytocin on the first study visit, with the other on the second.

**Study Visit 1:** The participant will report to the CTSI Clinical Research Unit (CRU) at least 3 days prior to study visit 2. The participant will review and sign the Informed Consent. After informed consent is adequately obtained, a detailed medical history will be obtained from the participant, female participants will have blood drawn and sent to the laboratory to determine pregnancy status. Participants will be trained to estimate pain quantitatively using a 2 cm^2 peltier controlled thermode (TSA®) applied to an area of normal skin outside the area of ongoing pain. Typically, the participant is exposed to temperatures between 38 and 51 C using a random staircase method.

During this training period, the participant's blood pressure, heart rate, and peripheral oxyhemoglobin saturation will be recorded. A 12 Lead electrocardiogram (ECG) will also be performed.

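### The going-home list does not carry through the protocol's own saturation threshold of 90, although desaturation is treated and rechecked elsewhere in the protocol

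*Combined protocol and SAP*

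**What the plan says.** The section Completion of Day 2 Assessment lists four conditions. It does not use the word discharge, but the items on an escort home and on staying reachable there show that this is its purpose. Item 1 reads "Vital signs are within 20% of those on admission to the CRU". Items 2 to 4 cover walking, the escort and staying at home.

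Safety and Monitoring sets the limits during the session: "Significant side effects are defined as changes > 30% from baseline in the mean arterial pressure, HR, or oxyhemoglobin pulse oximetry < 90". Mean arterial pressure and heart rate therefore have a relative limit, and saturation an absolute one. The treatment paragraph states "Peripheral oxyhemoglobin desaturation (< 90) will be treated with supplemental oxygen". When a change in blood pressure, heart rate or saturation requires treatment, "these vital signs will be repeated at 5-minute intervals until vital signs are stabilized". The measurement schedule is "Peripheral oxyhemoglobin saturation, BP and HR will be measured non-invasively before and 15, 30, 60, 120, 180, 240, minutes after administering spinal oxytocin".

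The section on Study Visit 4 applies the Visit 2 procedures again, so the list presumably governs both injection days.

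**The concern.** A going-home rule should be at least as strict as the rule that triggers treatment. For blood pressure and heart rate it is: 20% is tighter than 30%, provided the admission and baseline readings are similar. For saturation the order is reversed, because a 20% band around a normal saturation extends well below 90. It looks as though a percentage suited to blood pressure and heart rate was applied to vital signs in general.

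What is at stake is participant safety, not inference. The RISKS section names breathing among the things to be watched and concedes that the exact risks are unknown. The last scheduled saturation reading for an injection is at 240 minutes. The later contacts at 6 and 12 hours are telephone calls, and the visit at about 24 hours lists only a blood draw. Eligibility sets no saturation limit and excludes long-term oral opioids only above 100 mg morphine per day or equivalent, so some participants may be taking opioids at home.

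**Working it through.** **Inputs.** From the protocol: the 20% band (Completion of Day 2 Assessment, item 1); the saturation threshold of 90, the 30% threshold for mean arterial pressure and heart rate, and the 240-minute last reading (Safety and Monitoring); calls at 6 and 12 hours and a visit at about 24 hours (Completion of Day 2 Assessment and Study Visits 3 and 5). The protocol gives no admission saturation. I assume 95 to 100 and show 90 as a low case. There is no figure in the plan to reproduce.

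**Step 1: does item 1 cover saturation?** The text supports two readings.
- *Covered.* Safety and Monitoring names blood pressure, heart rate and saturation and then calls them vital signs ("these vital signs will be repeated at 5-minute intervals until vital signs are stabilized"). At Study Visit 1 the same three are taken together: "blood pressure, heart rate, and peripheral oxyhemoglobin saturation will be recorded".
- *Not covered.* The resting limits at entry name only two of them: "Blood pressure (systolic 90-150 mmHg; diastolic 50-90 mmHg) resting heart rate 45-100 beats per minute".

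The protocol does not define the term, so both readings are carried forward.

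**Step 2: lowest passing saturation if covered.** Floor = 0.80 × admission value.

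| Admission (assumed) | Floor, 20% relative | Points below 90 | Floor, 20 percentage points |
|---|---|---|---|
| 100 | 80.0 | 10.0 | 80 |
| 98 | 78.4 | 11.6 | 78 |
| 95 | 76.0 | 14.0 | 75 |
| 90 | 72.0 | 18.0 | 70 |

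A floor of 90 would need an admission value of 90 / 0.80 = 112.5, which is impossible. So a reading of 89 passes item 1 at every admission value from 90 to 100, whatever is assumed within that range. To exclude values below 90 by percentage alone, the band could be at most (100 − 90)/100 = 10.0% at an admission value of 100, or (95 − 90)/95 = 5.3% at 95.

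**Step 3: if not covered.** The floors above do not apply. Items 2 to 4 say nothing about saturation, so the list has no saturation condition.

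**Step 4: does another section supply the condition?** In part. Oxygen is required below 90, and rechecks follow if treatment is required. The rechecks end when vital signs are stable, which has no numeric definition. No section requires recovery to 90, or a reading off oxygen, before leaving. Read literally, a subject whose saturation is held up only by oxygen meets the list.

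**Step 5: time to the next contact.** From the reading at 240 minutes (4 hours): 6 − 4 = 2 hours to the first call, 12 − 4 = 8 hours to the second, and 24 − 4 = about 20 hours to the next visit. The next scheduled saturation reading is at Visit 4, at least 7 days after Visit 2. None is scheduled after Visit 4's own readings.

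**The case against.** The strongest reply is that the list should not be read alone. The oxygen instruction is unconditional, the method of delivery is adjusted to the response, and a treated subject is rechecked every 5 minutes. Nothing in the list cancels those duties. A reader might infer that the protocol lets a subject at 76 to 80 go home untreated. The documents do not support that: such a subject must be on oxygen under Safety and Monitoring, whatever item 1 says. This part of the objection stands and keeps the point small.

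A reader might also infer that saturation alone lacks a treatment end point, because blood pressure elevation has one ("until BP elevation is less than 30% elevated"). That does not hold either. Falls in blood pressure, and heart rate changes in either direction, have no stated end point. But for blood pressure and heart rate the 20% list item then acts as a backstop tighter than the treatment trigger. For saturation it does not.

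The floors of 72 to 80 rest on assumed admission values and on one of two readings. That is fair. The conclusion that the list has no floor at 90 depends on neither.

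Finally, little in the documents suggests that desaturation is likely. The Phase 1 study is reported without serious adverse events at 5 to 150 µg and with sensorium unaffected. No toxicity was observed in over 90 hip replacement subjects. In the investigators' earlier work mild respiratory depression is listed for fentanyl, not oxytocin. An anesthesiologist and a nurse are present, and the subject must walk without difficulty before leaving. All of this stands.

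**Conclusion.** The point holds as a gap in a written safety rule. The protocol treats and rechecks saturation below 90, but its going-home conditions do not carry that threshold through, and nothing requires a reading of at least 90 off oxygen before departure. If saturation is covered by the 20% limit, that limit lies 10 to 14 points below the treatment threshold for an assumed admission value of 95 to 100. If it is not covered, there is no limit.

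The practical effect is expected to be very small. The documents give no rate of desaturation, so the number of subjects affected cannot be estimated. The primary outcome and its analysis are untouched. I rate this at the lowest end of minor.

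**What to change.** For Visits 2 and 4, keep item 1 as written and add: *and oxyhemoglobin saturation is at least 90 without supplemental oxygen (or, if the admission value was below 90 or the subject uses home oxygen, is back to the admission value on the usual oxygen).*

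Keeping the general term in item 1 avoids dropping any other vital sign it was meant to cover. The bracketed exception is needed because eligibility sets no saturation limit and does not expressly exclude home oxygen. Without it, a subject with a low admission value might never qualify to leave.

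The cost is one clause, using the protocol's own threshold and measurements already taken up to 240 minutes. A subject who was given oxygen needs one room-air reading before leaving, and a stay in the CRU will occasionally be longer.
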